7.1.3	Recording of Adverse Events	"the safety follow-up period of 30 days after the last dose of investigational product" is amended to "the safety follow-up period of 90 days after the last dose of investigational product. AEs that occur after the safety follow-up visit can be recorded by telephone follow-up 60 days and 90 days after the last dose."	Adverse effects of an anti-PD-L1 or anti-PD-1 drug are primarily immune related events that last longer period of time. Prolonged period for AE collection will improve the safety management for subjects. Method of AE collection after the safety follow-up visit is defined.
7.2.2	Serious Adverse Events Reporting	"Any SAE occurring from the time of ICF signing to 30 days after the last dose of investigational product" is amended to "Any SAE occurring from the time of ICF signing to 90 days after the last dose of investigational product"	To correct a clerical mistake. "90 days" is in line with note 6 of Schedule of Study Activities.
6.4	Efficacy Assessment	"Bone marrow aspiration/biopsy should be performed when CR is achieved according to radiology" is amended to "Bone marrow aspiration/biopsy should be performed at screening. Subjects with positive bone marrow aspiration/biopsy result at screening will undergo bone marrow aspiration/biopsy when achieving CR based upon radiology."	According to Lugano classification, only subjects with positive baseline bone marrow need to have bone marrow test when CR is achieved according to radiology evaluation.
6.4	Efficacy Assessment	The sentence "PET/CT should be performed first followed by enhanced CT at screening, week 12 and week 24" is deleted.	The "PET/CT first and then enhanced CT" rule only applies to the situation where PET/CT and enhanced CT are performed on the same day. According to feedback from clinicians, PET/CT and enhanced CT are performed on separate dates in most cases. Therefore this requirement is deleted from the protocol, while a new requirement stating that "if PET/CT and enhanced CT are to be performed on the same day, PET/CT should be performed first followed by enhanced CT" is added in the Radiology Manual provided to the sites.
13.1	Criteria for Response Assessment of Lymphoma: Lugano 2014 Classification	In the "PD-New lesions" part, "A new node > 1.5 cm in any axis" is amended to "A new node > 1.5 cm in any axis (with an absolute increase of > 0.5 cm compared to the nadir value)"	The radiology evaluation criteria is refined after agreement is achieved with the central radiologists.

4.7.4	Laboratory Data	13
4.7.5	12-Lead Electrocardiogram (ECG)	13
4.7.6	ECOG Performance Status	14
4.7.7	Vital Signs	14
4.8	MISSING DATA	14
4.9	INTERIM ANALYSES	14
5. LIST OF ABB	REVIATION	14
APPENDIX 1 PR	COTOCOL SYNOPSIS	16
APPENDIX 2 SC	CHEDULE OF ASSESSMENTS	23
APPENDIX 3 HA	ANDLING OF MISSING DTAES	29
APPENDIX 4 SU	JMMARY OF CHANGES	30

BACKGROUND

[figure not shown]
This is a single-arm, multicenter, Phase II clinical trial to evaluate the efficacy and safety of CS1001 in subjects with R/R ENKTL.

STUDY DESIGN

PROTOCOL SYNOPSIS

The Protocol Synopsis is in Appendix 1. For additional details, see the Schedule of Assessments in Appendix 2.

DETERMINATION OF SAMPLE SIZE

ANALYSIS TIMING

Statistical analysis is planned to be performed by 24 weeks after the first dose of the last subject.

For US filing purpose, all the analyses will be repeated when all responders have at least 6 months follow-up from the date of first documented response.

[figure not shown]
STUDY CONDUCT

INDEPENDENT RADIOLOGICAL REVIEW COMMITTEE

Independent radiological review committee (IRRC) was adopted to provide the independent assessment to tumor response per Lugano 2014 classification. Independent review will be conducted as follows, with further details provided in the IRRC charter:

- Radiology Review: A radiology review period consists of the following review steps in the given sequence:
 - o Timepoint by Timepoint Radiology Review: Each imaging timepoint for a subject will be assessed by two independent reviewers that are board certified with relevant experience in radiology and nuclear medicine (double read), who will assess tumor burden at baseline and determine an overall tumor assessment at each post-baseline timepoint according to the Lugano Classification. Both CT/MRI and FDG-PET 5-point scoring assessments will be performed on the same electronic imaging case report form (eICRF). When FDG-PET is available, the Lugano Classification based overall tumor response will be based on CT/MRI and PET 5-point scoring. When FDG-PET is not available, the CT/MRI based assessments will drive the Lugano Classification based overall tumor response.
 - Global Radiology Review: Following completion of the timepoint by timepoint radiology review for a review period, the same independent reviewers that are dual board certified in radiology and nuclear medicine or have equivalent experience in both modalities will globally assess the reviewed timepoints and confirm or update their previous overall tumor assessments according to the Lugano Classification.
 - O Radiology Adjudication Review: Adjudication is required if the independent radiologists' results for a global radiology review are in disagreement as defined in IRRC charter 7.1 Radiology Adjudication Review Paradigm. During radiology adjudication review, an independent radiologist who did not participate in the timepoint by timepoint or global radiology review for the subject will choose the independent radiologist whose global radiology review assessments he/she agrees with most as the final assessment and provide justifying comments.
- Oncology Review: Following radiology review and adjudication review (if applicable) for a review period, one independent oncologist (single read) will review radiology review assessments and available clinical data and provide final tumor response assessments per visit, as defined in IRRC charter 8.7 Oncology Review Assessment Criteria.
- Secondary Radiology Review: The timepoint by timepoint radiology review and global radiology review for a subset of subjects will be repeated. Secondary radiology review is used for determination of intra-reader and/or inter-reader disagreement or variability for that subset of subjects and will not alter the original read. Further details on the secondary radiology reviews are provided in IRRC charter 12.1 Secondary Review.

This process is outlined in the following independent review workflow diagram:

STATISTICAL METHODS

GENERAL CONSIDERATIONS

All data processing, summarization, and analyses will be performed using Version 9.2 (or later) of the SAS® statistical software package.

In general, categorical data will be summarized using frequencies and percentages in each category, and continuous data will be summarized with descriptive statistics including the number of observations, mean, standard deviation (SD), median, minimum and maximum.

Baseline is defined as the last measurement before the first dose of the study drug.

ANALYSIS SETS

All analysis sets will be identified prior to database lock.

Efficacy Analysis Set (EAS)

Efficacy analysis set (EAS) consists of all subjects who received at least one dose of study drug and had been confirmed as ENKTL by central pathology

Safety Analysis Set (SAS)

Safety analysis set consists of all subjects who received at least one dose of study drug.

Pharmacokinetic Analysis Set (PKAS)

Pharmacokinetic analysis set consists of all subjects who received at least one dose of study drug and have available plasma drug concentration data.

Anti-drug Antibody Analysis Set (ADAAS)

Anti-drug antibody analysis set consists of subjects who received at least one dose of study drug and have available ADA data.

ANALYSIS OF STUDY CONDUCT

Patient Disposition

Subject status and reasons for treatment discontinuation and study discontinuation will be summarized. A listing will be provided for subjects who discontinued from treatment/study as well as the reasons.

The number and percentage of subjects in each analysis set will be summarized and listed.

Protocol Deviation

The major protocol deviations will be summarized and listed.

Prior and Concomitant Medications

Prior and concomitant medications will be coded using WHO Drug Dictionary (WHODD) latest version and they will be summarized separately following below definitions for subjects in the safety analysis set:

- Prior medications are defined as medications ended before study drug initiation
- Concomitant medications are defined as medications ongoing or started after study drug initiation.

DEMOGRAPHIC AND BASELINE CHARACTERISTICS

Demographic and baseline characteristics will be summarized for subjects in the safety analysis set.

Demographic

The demographic data, including but not limited to age, sex, race, ethnicity, will be summarized for safety analysis set.

Baseline Characteristics

Tumor diagnosis, including but not limited to staging, central pathology results will be summarized and listed for safety analysis set.

Medical history (other than study disease) will be coded with Medical Dictionary for Regulatory Activities (MedDRA) and summarized by system organ class (SOC) and preferred term (PT) for safety analysis set.

Prior Cancer Therapy

Prior systemic cancer therapy will be coded with WHODD and summarized by ATC terms for safety analysis set.

Prior radiotherapy and prior cancer-related surgery/procedure will be summarized for the safety analysis set.

EFFICACY ANALYSES

The analyses of efficacy endpoints are based on the efficacy analysis set.

Primary Efficacy Endpoint

The primary efficacy endpoint is ORR by IRRC based upon Lugano 2014 classification, defined as the proportion of subjects who achieve complete response (CR) or partial response (PR) as the best overall response. Subjects who did not have any post-baseline tumor assessment will be considered as non-responders.

The IRRC-ORR analysis will include subjects with evaluable or measurable lesion at baseline as confirmed by IRRC in EAS.

The 95% CI of ORR will be calculated using the exact binomial (Clopper-Pearson) method to evaluate the precision of the ORR estimate.

Secondary Efficacy Endpoints

The ORR assessed by investigators will be analyzed and provided as described in Section 0. Proportions of subjects who achieve CR, PR, stable disease (SD), and progressive disease (PD) per IRRC evaluation and their 95% CIs will be summarized. This analysis will be performed for subjects with evaluable or measurable lesion at baseline as confirmed by IRRC in EAS. Proportions of subjects with responses per investigator's evaluation and their 95% CIs will also be summarized as for IRRC. This analysis will be performed for subjects with evaluable or measurable lesion at baseline as confirmed by investigators in EAS.

Duration of response (DoR) is defined as the time from the first documented CR or PR (whichever comes first) to the first documented disease progression or death, whichever comes first. DoR will be evaluated in subjects with objective responses per investigator's or IRRC's assessment, respectively. Subjects without event (disease progression or death) as of data cutoff will be censored at the date of the last tumor assessment. If no tumor assessment is performed after the first occurrence of CR or PR, DoR will be censored at the date of first CR or PR. Subjects with subsequent anti-cancer therapy(if any) before event will be cencored at the date of last tumor assessment prior to the initiation of therapy. If an event is observed immediately after two or more consecutive missed tumor assessments, subjects will be censored at the date of last tumor assessment prior to the missing tumor assessments. Kaplan-Meier methodology will be used to analyze DoR and the KM curve will be constructed.

Time to response (TTR) is defined as the time from the first study dose to the first documented CR or PR, whichever comes first. TTR will only be evaluated for subjects

who achieve a response. TTR will be summarized according to the investigator's and IRRC's assessments, respectively.

Progression-free survival (PFS) in months is defined as the time from the date of the first dose to the date of first documented disease progression or death, whichever comes first. The investigators and IRRC will assess the progression of disease based upon the Lugano 2014 classification. Subjects without an event (disease progression or death) will be censored at the date of the last tumor assessment. Subjects without tumor assessment after baseline will be censored at the date of the first dose. 6-month PFS rate refers to the proportion of subjects who are alive without any progression or death at 6 months after the first dose of study drug. 6-month PFS rate will be calculated using the Kaplan-Meier method and the Greenwood formula will be used to derive the variance for the 95% CI calculation.

Overall survival (OS) is defined as the time from the date of the first dose to the date of death from any cause. Subjects without death will be censored at the date of the last date known to be alive. Subjects without any data after baseline will be censored at the date of the first dose. The detailed analysis methodology described for PFS will also be used for the analysis of OS.

Sensitivity Analyses

The IRRC-ORR analysis will be repeated for subjects in the safety analysis set.

Subgroup Analyses

Subjects will be grouped based upon their demographics (for example age, sex) and baseline characteristics (for example ECOG PS, prior treatment lines) to evaluate the consistency among all subgroups

Exploratory Analyses

Exploratory analysis will be performed to identify the relationship between biomarkers and the efficacy of the study drug. The consistency of ORR (yes or no) between IRRC evaluation and investigator's evaluation will also be assessed.

PHARMACOKINETIC AND PHARMACODYNAMIC ANALYSES

Pharmacokinetic Analyses

Descriptive analysis will be performed for serum concentration of CS1001 in samples taken at planned sampling time points. The data in this study will be pooled with that from other CS1001 trials to develop a population PK model. This model will be used to evaluate internal and external covariates and their influence on the PK of CS1001. Furthermore, the exposure-response analysis will be performed on specific efficacy and safety endpoints. Separate analysis plans will be developed for the population PK analysis and exposure response analysis. Results of the above group PK and exposure-response analyses will be recorded in separate reports.

Immunogenicity Analyses

Immunogenicity evaluation results will be reported for the following parameters. Number and percentage of subjects who have positive anti-drug antibody (ADA) at baseline; number and percentage of subjects with at least one positive ADA test result in any time point following the first dose of study drug; number and percentage of subjects who develop treatment-induced ADA any time after the first dose of study drug; number and percentage of subjects with treatment-enhanced ADA any time after the first dose of study drug.

Treatment-induced ADA positive is defined as: Patients who had a baseline-negative ADA result and at least one positive ADA result at any time after first study drug administration.

Treatment-enhanced ADA positive is defined as: Patients who had a baseline-positive ADA result and at least one enhanced (greater than baseline fourfold) result at any time after first study drug administration.

Treatment unaffected ADA is defined as: Patient with positive ADA results at baseline and all post-baseline titer result are not greater than fourfold the baseline titer result or

Patient with positive ADA results at baseline and all post-baseline results are negative or missing.

For subjects who are confirmed positive ADA, further testing will be performed for ADA neutralizing antibody (NAb). The following additional summaries will be provided:

- Number and percentage of subjects who have positive ADA neutralizing antibody (NAb) test result at baseline.
- Number and percentage of subjects who have at least one positive NAb test result at any time point following the first dose of investigational product.

SAFETY ANALYSES

The safety analyses will be based on the safety analysis set.

Exposure of Study Medication

Descriptive statistics will be performed to summarize the exposure to study drug, including duration of treatment exposure in months, number of cycles, cumulative actual dose. etc.

Adverse Events

All AEs will be coded using the MedDRA dictionary. The severity will be graded using the National Cancer Institute (NCI) Common Terminology Criteria for Adverse Events (CTCAE), version 4.03.

The number of subjects experiencing treatment-emergent adverse events (TEAEs) will be summarized. TEAE was defined as:

- AE occurred on or after study treatment initiation or
- AE occurred before study treatment initiation but worsened on or after study treatment initiation

In addition, serious TEAEs, severe TEAEs (Grade ≥ 3), treatment-related TEAEs, immune-related TEAEs (assessed by the investigator), infusion-related reactions, and TEAEs leading to study drug discontinuation or interruption will also be summarized.

A subject experiencing multiple AEs under the same PT or SOC will be counted only once for that PT or SOC by maximum severity.

Adverse events of special interest (AESIs) will be assessed by the sponsor. The following summaries will be provided:

- For each AESI category, the number and percentage of subjects who experienced at least one of the following events will be summarized by treatment group: AESI, serious AESI, AESI with NCI-CTCAE grades 3-5, immune-related adverse events evaluated by investigator, AESIs resulting in CS1001/placebo discontinuation, AESIs resulting in CS1001/placebo interruption (including AESIs resulting in delayed treatment cycle of CS1001/placebo), AESIs resulting in death, AESIs requiring systemic corticosteroid, and AESIs requiring high-dose systemic corticosteroid.
- AESIs by the most serious NCI-CTCAE grade, PT and treatment group will be summarized.
- AESIs by PT, outcome of adverse events and treatment group will be summarized.
- Time to onset and duration of each AESI will be summarized using Kaplan-Meier method.
- The number and percentage of subjects who experienced thyroid or diabetes mellitus related AESI at least once and used corresponding concomitant medications will be summarized.

All AEs will be listed by subject.

Death

Death reasons will be summarized. All deaths will be listed by subject.

Laboratory Data

The laboratory data will be converted to Standard International (SI) units. The absolute value and change from baseline of each lab parameters will be summarized by scheduled visit.

Grading of laboratory data

Laboratory data will be derived programmatically according to the NCI CTCAE version 4.03. The calculation of CTC grades will be based on the observed laboratory values only, clinical assessments will not be considered. A shift table will be produced to reflect the grade change at the worst post-baseline assessment from the baseline visit.

Liver function parameters

The number and percentage of subjects with Liver Function Laboratory Findings will be summarized based on the event criteria as below:

Parameter	Criteria
ALT	>3xULN; >=5xULN; >=10xULN; >=20xULN
AST	>3xULN; >=5xULN; >=10xULN; >=20xULN
ALT or AST	>3xULN; >=5xULN; >=10xULN; >=20xULN
Total bilirubin (TBIL)	>=1.5xULN; >=2xULN
ALP	>=1.5xULN
ALT and/or AST & TBIL	ALT and/or AST>3xULN & TBIL >=1.5xULN ALT and/or AST>3xULN & TBIL >=2xULN
ALT and/or AST & TBIL & ALP	ALT and/or AST>3xULN & TBIL >=2xULN & ALP <2xULN

For a combined criterion to be fulfilled, all conditions have to be fulfilled on the same visit. The criteria are not mutually exclusive, e.g., a subject with ALT = 6.42xULN is counted for ALT >3xULN and ALT>5xULN.

12-Lead Electrocardiogram (ECG)

The analyses of 12-lead ECG data are based on the safety analysis set.

Overall interpretation of 12-lead ECG results will be summarized by visit.

Patient listing of clinically significant abnormal 12-lead ECG results will be provided.

ECOG Performance Status

The analyses of ECOG performance status are based on the safety analysis set.

Shift table will be produced for ECOG performance status at highest post-baseline visits and baseline.

Vital Signs

The analyses of vital signs are based on the safety analysis set.

Each vital sign parameter at each visit will be summarized, along with the absolute change from baseline.

MISSING DATA

The imputation for missing results will not be performed. The censoring rules for efficacy endpoints can be found in section 4.5.

Missing/Incomplete dates will be imputed according to Appendix 3. The output of listings will display the dates before imputation.

INTERIM ANALYSES

No formal efficacy interim analyses are planned.

LIST OF ABBREVIATION

Abbreviation	Full Name of Abbreviation
ADA	Anti-drug Antibody
ADAAS	Anti-drug Antibody Analysis Set
CI	Confidence Interval
CR	Complete Response
CT	Computed Tomography
CTCAE	Common Terminology Criteria for Adverse Events
CV	Coefficient of Variation
DoR	Duration of Response
EAS	Efficacy Analysis Set
ECOG	Eastern Cooperative Oncology Group
eICRF	Electronic Imaging Case Report Form
eOCRF	Electronic Oncology Case Report Form
FDG	Fluorodeoxyglucose
IRRC	Independent Radiological Review Committee
MRI	Magnetic Resonance Imaging
NAb	Neutralizing antibody
NCI	National Cancer Institute
OS	Overall Survival
PD	Progression
PD-1	Programmed Death-1
PD-L1	Programmed Death Ligand 1

Abbreviation	Full Name of Abbreviation
PET	Positron Emission Tomography
PFS	Progression-Free Survival
PK	Pharmacokinetics
PKAS	Pharmacokinetics Analysis Set
PR	Partial response
PT	Preferred Term
R/R ENKTL	Relapse Or Refractory Extranodal Natural Killer / T cell lymphoma
SAS	Safety Analysis Set
SD	Stable Disease
SOC	System Organ Class
TBIL	Total Bilirubin
TEAE	Treatment-Emergent Adverse Event
TTR	Time To Response
ULN	Upper limited normal
UNK	Unknown
WHODD	WHO Drug Dictionary

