2. OBJECTIVES AND ENDPOINTS

Objectives	Endpoints
Primary objectives	Primary endpoints
To evaluate the efficacy of CS1001 in subjects with R/R ENKTL;	Objective response rate (ORR) assessed by IRRC according to Lugano 2014 classification
Secondary objectives	Secondary endpoints
To evaluate the efficacy of CS1001 in subjects with R/R ENKTL;	ORR assessed by investigators; CRR, PRR, TTR, DoR assessed by IRRC and investigators;
To evaluate the safety of CS1001 in subjects with R/R ENKTL	Severity and frequency of AEs, and frequency of SAEs
To evaluate the PK of CS1001	To determine the peak and trough serum concentration of CS1001
To evaluate the immunogenicity of CS1001	Number and percentage of subjects who develop ADA
Exploratory objectives	Exploratory endpoints
To evaluate the progression-free survival (PFS) and overall survival (OS) of R/R ENKTL subjects	6-months PFS rate, 6-month OS rate
To evaluate genetic aberrations in R/R ENKTL by whole-exome sequencing test of tumor tissues	The association between genetic aberrations and efficacy

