8.7 EXPLORATORY ANALYSES

Progression-free survival (PFS) and overall survival (OS) will be explored. PFS is defined as the time from the first study dose to the date of first documented disease progression or death, whichever comes first. The investigators and IRRC will assess the progression of disease based upon the Lugano 2014 classification. At the analysis, subjects without event (disease progression or death) will be censored at the date of "last tumor assessment". Subjects without tumor assessment after baseline will be censored at the date of the first dose. Six-month PFS rate refers to the proportion of subjects who are alive without any progression at 6 months after the first dose of investigational product. Six-month PFS rate will be calculated using the Kaplan-Meier method and the Greenwood formula was used to derive the variance regarding its 95% CI calculation.

OS is defined as the time from the first study dose to the date of death irrespective of its cause. Subjects without death reports as of data cutoff will be censored at the date of the last survival confirmation. Subjects without any data after baseline will be censored at the date of the first dose. The same analysis method is used for PFS.

Exploratory biomarker analysis will be performed to identify the relationship between tumor genetic aberrations and the efficacy of the investigational product. Subjects will be subgrouped based upon their demographics (for example age, sex) and baseline characteristics (for example ECOG PS, prior treatment lines) for evaluating the consistency among all subgroups.

The consistency of ORR (yes or no) between IRRC evaluation and investigator's evaluation will also be assessed.

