Neuromuscular toxicity	Peripheral sensory neuropathy, muscle weakness, Guilliain- Barre syndrome, transverse myelitis, myasthenia gravis	 Physical exam of sensory change, loss of deep- tendon reflexes Neuroimaging, nerve conduction exam 	≤ Moderate (Grade 2): administration of corticosteroids at a dose of 1-2 mg/kg/day prednisone equivalents	Withhold CS1001 until resolved to ≤ Grade 1
	 conduction exam Nerve/muscle biopsy 		≥ Severe (Grade 3): high dose corticosteroids (2-4 mg/kg/day IV methylprednisolone)	Permanent discontinuation from the study treatment

Potential irAE	Potential signs and symptoms	Diagnosis and differential diagnosis	Recommended management	Dose modification
Ocular toxicity	Photosensitivity, pain or dryness of the eyes, blurred vision, uveitis, iritis, episcleritis	• Ophthalmic exam	≤ Moderate (Grade 2): topical steroids (1% prednisolone)	Withhold CS1001 until resolved to \leq Grade 1; if not resolved \leq Grade 1 within 14 days with topical steroids or initiation of systemic treatment, permanent discontinuation from the study treatment
			≥ Severe (Grade 3): high dose corticosteroids (2-4 mg/kg/day IV methylprednisolone)	Permanent discontinuation from the study treatment
Other irAEs, such as arthritis, pancreatitis, hemolytic anemia,			Moderate (Grade 2)	Withhold CS1001 until resolved to \leq Grade 1
adrenal insufficiency, myasthenic syndrome, and rhabdomyolysis			≥ Severe (Grade 3)	Permanent discontinuation from the study treatment

13.5PROTOCOL AMENDMENT

Major amendments in protocol Version 3.0

Section(s)	Title of section(s)	Amendment details	Amendment rationale
SYNOPSIS	Secondary endpoints	Move 6 month PFS and 6 month OS rate from secondary endpoints to exploratory endpoints,	In single-arm trials, time-to-event efficacy endpoints such as PFS and OS
	Secondary efficacy analyses	details refer to Protocol Amendment 3.0	should be exploratory rather than secondary endpoints
	Exploratory endpoints		secondary enapoints
	Exploratory efficacy analyses		

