The statistical analysis will be performed by 24 weeks after the first dose of last subject.

Secondary efficacy analyses:

Proportions of subjects who achieve CR, PR, SD, and PD per IRRC evaluation and their 95% CIs will be summarized. This analysis will be performed in EAS subjects with evaluable or measurable lesion at baseline judged by IRRC. Proportions of subjects with responses per investigator's evaluation and their 95% CIs will be summarized. This analysis will be performed in EAS subjects with evaluable or measurable lesion at baseline judged by investigators.

Duration of response (DoR) is defined as the time from the date of the first documented CR or PR (whichever comes first) to the date of the first documented disease progression or death, whichever comes first. DoR will be evaluated in subjects with objective responses per investigator's or IRRC's assessment, respectively.

Time to response (TTR) is defined as the time from the date of the first study dose to the date of the first documented CR or PR, whichever comes first. TTR will only be evaluated for subjects who achieve ORR. TTR will be summarized according to the investigator's and IRRC's assessment, respectively.

Kaplan-Meier method will be used to analyze DoR; KM plots will be provided. DoR analysis will only be performed in subjects with objective responses.

Exploratory efficacy analyses:

Progression-free survival (PFS) is defined as the time from the date of the first study dose to the date of first documented disease progression or death, whichever comes first.

Overall survival (OS) is defined as the time from the date of the first study dose to the date of death irrespective of its cause.

Kaplan-Meier method will be used to analyze PFS and OS.

Sample size:

Pharmacokinetic analysis:

Descriptive statistics will be summarized for the serum concentration of CS1001 for blood samples taken at pre-specified time points.

Safety analysis:

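### Does it matter that the SAP body files PFS and OS under secondary endpoints and gives DoR two censoring rules that PFS lacks?

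*SAP*

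**What the plan says.** **Rank.** In the SAP body, the section Secondary Efficacy Endpoints runs through investigator ORR, the response categories, DoR and TTR, then PFS ("Progression-free survival (PFS) in months is defined as the time from the date of the first dose") and OS. The next heading is Sensitivity Analyses. The later Exploratory Analyses paragraph covers biomarkers ("Exploratory analysis will be performed to identify the relationship between biomarkers and the efficacy of the study drug") and agreement between IRRC and investigator, and mentions neither PFS nor OS.

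Protocol Section 2 lists "6-months PFS rate, 6-month OS rate" as exploratory endpoints, and Protocol 8.7 states "Progression-free survival (PFS) and overall survival (OS) will be explored". SAP Appendix 1 repeats that endpoint table and, under exploratory efficacy analyses, says "Kaplan-Meier method will be used to analyze PFS and OS".

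**Censoring.** For PFS the SAP says "Subjects without an event (disease progression or death) will be censored at the date of the last tumor assessment", and a subject with no post-baseline assessment is censored at first dose. The DoR paragraph has the equivalent basic rules plus two more: censor at the last assessment before new anti-cancer therapy, and censor at the last assessment before two or more consecutive missed ones when the event follows directly. SAP Appendix 4 records these two as additions for DoR, made after regulator comments.

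**The concern.** Current texts disagree about the class of two endpoints, and the SAP disagrees with itself. The move in Protocol v3.0 was deliberate. Its amendment table reads "Move 6 month PFS and 6 month OS rate from secondary endpoints to exploratory endpoints", and the rationale, opening "In single-arm trials, time-to-event efficacy endpoints such as PFS and OS", goes on to say that these belong among the exploratory endpoints. A report programmed only from the SAP body could give PFS and OS a standing in a single-arm trial that the sponsor had withdrawn.

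The censoring difference raises a second doubt. In Protocol 8.3.2, 8.7 and 8.8, DoR and PFS follow parallel rules. In the SAP, a responder who starts another therapy and then dies is censored for DoR but counts as an event for PFS. Protocol 3.2.2 says ORR will be read together with PFS and DoR, so readers will compare them and may wonder whether PFS was overlooked.

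**Working it through.** **1. Rank, side by side**

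| Place | Class of PFS and OS |
|---|---|
| Protocol Section 2 | Exploratory |
| Protocol 8.3.2 (secondary) | Not listed |
| Protocol 8.7 | Exploratory |
| SAP Appendix 1 | Exploratory |
| SAP body | Secondary |

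The SAP body is the only one out of line. SAP Appendix 4 explains how this probably arose: it records Appendices 1 and 2 as updated to protocol 3.0, but for Section 4.5.2 it lists only the DoR rules.

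**2. What depends on the rank**

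- Population: the SAP bases efficacy endpoints on the efficacy analysis set, whatever their class.
- Estimator: Kaplan-Meier with Greenwood variance for the 6-month rate, in both Protocol 8.7 and the SAP body.
- Inference: no test, alpha or testing order for secondary or exploratory endpoints in the visible text.

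The change in any estimate, interval or error rate from moving the paragraphs is therefore zero.

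**3. Whether the censoring is ambiguous**

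The SAP's Missing Data section sends the reader to Section 4.5 for the efficacy censoring rules. The two added rules appear there only in the DoR paragraph, and the change log names DoR. A programmer has one reading: they do not apply to PFS. That agrees with Protocol 8.7 and 8.8.

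**4. How much a different PFS rule would matter**

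The documents do not say how many subjects switch therapy before an event, so this is illustration only. Assumptions: 80 subjects (the planned enrolment; the efficacy set may be smaller), exponential PFS, follow-up uniform on 6 to 30 months, switching at a uniform time before the event, 12-weekly scans, 1,000 simulated data sets per row.

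| Median PFS | Share switching | 6-month PFS, rule as written | With the new-therapy rule | Shift (points) |
|---|---|---|---|---|
| 3 months | 5% | 24.9% | 25.4% | 0.5 |
| 3 months | 10% | 25.0% | 26.0% | 1.1 |
| 3 months | 20% | 24.8% | 27.3% | 2.5 |
| 6 months | 5% | 50.1% | 51.0% | 0.9 |
| 6 months | 10% | 49.7% | 51.4% | 1.7 |
| 6 months | 20% | 49.7% | 53.4% | 3.7 |

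Shifts were taken before rounding. For scale, the standard error at 50% is √(0.5 × 0.5 / 80) = 5.6 points, and at 25% it is √(0.25 × 0.75 / 80) = 4.8 points. The largest shift is 3.7 / 5.6 ≈ 0.7 standard errors.

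The missed-scan rule has little reach at six months. Two missed 12-weekly scans put the next scheduled one 3 × 12 = 36 weeks after the last, whereas six months is about 26 weeks. Only a death or unscheduled finding between Week 24 and about Week 26, after both the Week 12 and Week 24 scans were missed, could bring it into play.

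**5. A bound that does not hold**

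It is tempting to say one affected subject moves the 6-month rate by at most 1/n, or 1/80 = 1.25 points. That needs no other censoring before Month 6. Take 30 early events among 80, so the curve stands at 50/80 = 0.625. One subject is clear at Week 24 (168 / 30.4375 = 5.52 months), switches, and dies at 5.9 months. PFS as written drops by 0.625 / r, where r is the number at risk; a DoR-style rule leaves the curve where it was.

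- No other censoring, r = 50: 0.625 / 50 = 1.25 points.
- Ten others censored after the early events, r = 40: 0.625 / 40 = 1.56 points.
- Twenty others, r = 30: 0.625 / 30 = 2.08 points.

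Nor does a clear Week 24 scan remove a subject's influence. With 50 early events and no other censoring, the same death gives 29/80 = 36.25% against 30/80 = 37.5%.

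**The case for a change.** The best case for a change is that it is cheap and follows the sponsor's own amendment. The SAP body is what programmers work from, and its Analysis Timing section has all analyses repeated for a US filing. Moving two paragraphs would end the contradiction, and one sentence would confirm that the extra censoring is for DoR only.

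What stands: the classification is inconsistent, nothing in the documents defends the secondary rank, and DoR and PFS will treat some responders differently.

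What does not stand is the need for action. The right class is in the current protocol and inside the same SAP, so a report author has to overlook both to go wrong. A confirming sentence would only restate what the placement of the rules and the change log already settle. A sentence saying that PFS counts every progression whatever therapy came before would also promise too much. Protocol 3.1.3 and 6.4 end scheduled tumor assessment at new anti-cancer treatment while survival follow-up goes on, so events recorded after a switch would be mainly deaths. An added sensitivity table would address a difference that is not an error, in an exploratory endpoint.

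**Conclusion.** No change is needed. The rank is a clerical slip with zero effect on any estimate, interval, test or conclusion. Report authors can follow Protocol v3.0 and SAP Appendix 1, which agree. The censoring difference is a determinate choice consistent with the protocol.

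The 0.5 to 3.7 points describe a rule the plan did not adopt. They rest on the assumed 80 subjects, exponential PFS, and switching rates and times that the documents do not give. They also treat every event after a switch as observed, which is more than the scan schedule provides, so they probably overstate the number of subjects affected. The conclusion on rank rests on the visible text, which shows no testing hierarchy for these endpoints.
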